8.4 Interim Analysis

One interim analysis will be performed.

The interim analysis will be conducted by the study team when all subjects have completed the double-blind phase (Visit 5 - Week 12). The database will be locked and unblinded to assess for efficacy and safety. The results will be reported in the clinical study report (CSR).

In the event of early stopping due to interim analysis results, subjects will be brought to the investigational sites for a final visit. The final analysis will include all data collected up to and including the final visit.

8.5 Analysis of Efficacy

All original and derived efficacy parameters as well as population characteristics will be described using summary statistics. All primary and secondary efficacy endpoints will be analyzed for pairwise differences between treatment groups.

8.5.1 Primary Efficacy Endpoint(s)

The primary efficacy endpoint will be the proportion of subjects with a clinical response of treatment success on Week 12. Treatment success is defined as:

At least a 2-grade improvement on the Week 12 Investigator Global Assessment (IGA) of the facial skin lesions assessed by investigator. The primary efficacy endpoint will be analyzed using Fisher's exact test, making all pairwise treatment comparisons.

8.5.2 Secondary Efficacy Endpoints

Secondary efficacy endpoints will be the following:

- The proportion of subjects with an investigator assessed IGA score of clear or almost clear with at least a 2-grade improvement on the Week 12 IGA of the facial skin lesions;
- The proportion of subjects with at least 30% improvement at Week 12 as compared to Baseline in the Facial Angiofibromas Severity Index (FASI) score, which is based on lesion erythema, size, and extension (Salido et.al. 2012);²⁰
- The time to reach at least 30% improvement from Baseline in the FASI score for angiofibroma severity;
- The proportion of subjects with at least 2-grade improvement at Week 12 as compared to Baseline in categorical lesion counts (scored as follows: No lesion = 0; <25 lesions = 1; 25-50 lesions = 2; 51-75 lesions = 3, >75 lesions = 4);
- The proportion of subjects with at least 2-grade improvement at Week 12 as compared to Baseline in lesion elevation score;
- The proportion of subjects with at least 2-grade improvement at Week 12 as compared to Baseline in the subject self-assessment survey;
- Overall Response of angiofibroma assessed by the investigator at Week 12 as compared to baseline based on Modified Nobel Scoring System;
- Overall Response of angiofibroma assessed by the IRC at Week 12 as compared to baseline based on Modified Nobel Scoring System;

- The proportion of subjects with at least Moderate Improvement (a score of 2) on Modified Nobel Scoring System assessed by the investigator at Week 12;
- The proportion of subjects with at least Moderate Improvement (a score of 2) on Modified Nobel Scoring System assessed by the IRC at Week 12;
- The proportion of subjects with at least a 2-grade improvement on Week 12 Investigator Global Assessment (IGA) of the facial skin lesions assessed by the IRC.

Treatment comparison of the proportion of treatment success with clear or almost clear will be conducted using Fisher's exact test at each time point, making all pair-wise comparisons. Descriptive statistics for observed values, absolute changes, and percent changes from Baseline (for FASI lesion score) and Number and percentage of subjects reached each overall response level for Modified Nobel Scoring System score will be summarized by treatment group at each time point. Student's t-test will be used for pairwise comparison of continuous endpoints at each time point. Wilcoxon rank sum test will be used to compare Modified Nobel Scoring System score. Fisher's exact test will be used for categorical endpoints. Time to reach at least 30% improvement from Baseline in the FASI score will be analyzed using Kaplan-Meier method, making all pairwise treatment comparisons. Proportion of subjects with at least Moderate Improvement on Modified Nobel Scoring System will be analyzed using Fisher's exact test, making all pair-wise comparison. Proportion of subjects with at least a 2-grade improvement on the Week 12 IGA will be analyzed using Fisher's exact test, making all pair-wise comparisons.

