7.2.2 Visit 2 Randomization/Baseline (Day 1)

- Review inclusion and exclusion criteria to ensure that the subject is qualified for study participation, including laboratory test results from Visit 1.
- Review and record medication used since the Screening visit.
- Record any new medical history since the Screening visit.
- Measure vital signs (systolic and diastolic blood pressure, heart rate, and respiratory rate) with subject in a seated position.
- Perform a UPT for females of childbearing potential. Remind sexually-active female subjects of childbearing potential to use approved method(s) of contraception. Remind sexually active male subjects that they (or their female partners) should use appropriate contraception. (In the unlikely event that a urine pregnancy test cannot be obtained, a serum pregnancy test can be run from the serum sample collected.) (For China, different pregnancy test procedure would be followed).
- Perform the following efficacy assessments:
 - Investigator's Global Assessment (IGA);
 - Facial Angiofibroma Severity Index (FASI) (assessment of erythema, size, and extension);
 - Modified Nobel Scoring System (assessment of target lesions and non-target lesions response);
 - Categorical lesion count using the following categories: (0) no lesion; (1) <25 lesions; (2) 25-50 lesions; (3) 51-75 lesions; (4) >75 lesions.
 - Assessment of lesion elevation.
- Have the subject (or parent/guardian for subjects under the developmental age of 7 years) complete the subject self-assessment survey.
- Take a photograph of the angiofibroma according to the Standardized Operation Procedure ([Appendix 2](#)).
- Record any AEs.

- Perform randomization by sequentially choosing the kit with the lowest randomization number.
- Weigh the study medication and dispense to the subject or their parent/guardian with dosing instructions.
- Dispense the dosing diary to the subject or parent/guardian.
- Schedule the next visit; instruct the subjects to bring the study medication to the study visit.

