7.3.2 Secondary Efficacy Assessment: Facial Angiofibroma Severity Index (FASI)

At study visits (Visit 1 through Visit 3, Visit 5 Visit 8 and Early Termination), the investigator will grade the treatment area for erythema, average size, and degree of involved skin (lesion extension). The grades for erythema, size, and extension are presented in [Table 7-2](#). A composite score, the Facial Angiofibromas Severity Index (FASI), will be derived from these measurements.

Table 7-2 Scoring for Erythema, Size, and Extension

Score	Description
Erythema	
0	Clear skin with no signs of erythema
1	Almost clear; slight redness
2	Mild erythema; definite redness
3	Moderate erythema; marked redness
4	Severe erythema; very bright redness
Size	
0	No lesions
1	Few lesions, average lesion size \leq 2mm
2	Scattered, some lesions, average lesion size >2 to \leq 5mm
3	Concentrated, many lesions, average lesion size >5mm to \leq 10mm
4	Confluent, highly concentrated lesions
Extension	
0	No lesions
2	\leq 50% of the cheek surface
3	> 50% of the cheek surface

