8.0 STATISTICAL METHODS AND DETERMINATION OF SAMPLE SIZE STATISTICAL AND ANALYTICAL PLANS

8.1 General Considerations for Data Analysis

The methodology presented below represents a brief overview of the statistical methods that will be fully detailed in the statistical analysis plan (SAP). The SAP will be finalized before the database is locked and unblinded. Any changes to the methods described in the final SAP will be described and justified in the clinical study report. It is planned that the data from all centers that participate in this protocol will be combined so that an adequate number of subjects will be available for analysis. All statistical analyses will be performed using SAS statistical software (Version 9.2 above).

Statistical significance will be tested at the 2-sided 5% level. No adjustments for multiplicity are planned.

All efficacy and safety analyses will be performed on observed data with no imputation unless otherwise specified. For the analyses of treatment response, subjects having a missing responder status will be analyzed as non-responders.

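### The supportive FASI comparison uses an unadjusted t-test although baseline FASI is collected; ANCOVA on baseline would usually be more efficient

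*Combined protocol and SAP*

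**What the plan says.** Section 8.5.2 and the Statistical Methods part of the synopsis carry the same sentence: "Student's t-test will be used for pairwise comparison of continuous endpoints at each time point". The sentence does not name FASI. The sentence before it in Section 8.5.2 lists "Descriptive statistics for observed values, absolute changes, and percent changes from Baseline (for FASI lesion score"), and FASI is the only score summarised that way. Those three quantities are for description; nothing says which one is tested. No covariate is mentioned.

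Section 7.2.2 has the investigator perform the "Facial Angiofibroma Severity Index (FASI) (assessment of erythema, size, and extension") at Visit 2, before dosing. Section 7.3.2 says "A composite score, the Facial Angiofibromas Severity Index (FASI), will be derived from these measurements" and gives no combining formula. In the double-blind period the later FASI visits are Weeks 4 and 12.

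The FASI endpoints listed in Section 8.5.2 are a 30% responder rate at Week 12 and "The time to reach at least 30% improvement from Baseline in the FASI score for angiofibroma severity". Neither is continuous.

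Section 8.1 describes itself as text that "represents a brief overview of the statistical methods that will be fully detailed in the statistical analysis plan (SAP"), and says the SAP will be final before lock and unblinding. No further SAP text is in the documents provided.

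**The concern.** A t-test that ignores baseline leaves unused a measurement that is already in the database. Its efficiency also depends on which quantity is tested. A test on the Week 12 score gains nothing from a strong baseline correlation, and a test on change loses power when the correlation is weak. The documents give no correlation, so the better of the two cannot be picked in advance. ANCOVA avoids the choice because it estimates the baseline slope from the data.

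What is at stake is the precision of a supportive comparison with about 15 subjects per arm. The validity of the trial's conclusions is not in question.

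**Working it through.** **The plan's own figure.** There is none to reproduce. Section 8.2 says the sample size has no statistical basis. The only arithmetic is 45/3 = 15 per arm under 1:1:1 allocation.

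**Inputs.** From the documents: 15 per arm, two-sided 5% level (Section 8.1), baseline FASI at Visit 2. Assumed: a true difference of 0.9 SD for 0.4% against placebo, the same SD at both visits, normal data, and a baseline to Week 12 correlation ρ between 0.1 and 0.9.

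**Formulas.** In units of the Week 12 variance, the variance V is:
- t-test on the Week 12 score: V = 1
- t-test on change: V = 2(1 − ρ)
- ANCOVA: V = 1 − ρ²

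Power comes from the noncentral t with noncentrality d / √(V × k × 2/15). For the t-tests k = 1 with 28 df. For the three-arm ANCOVA k = 1 + 1/40 = 1.025, for chance baseline imbalance, with 45 − 3 − 1 = 41 df.

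**Worked case, ρ = 0.5, d = 0.9.**
- Week 12 score: 0.9/√(1 × 2/15) = 0.9/0.365 = 2.46, power 66%.
- Change: V = 2 × 0.5 = 1, so again 2.46 and 66%.
- ANCOVA: V = 0.75; 0.9/√(0.75 × 1.025 × 2/15) = 0.9/0.320 = 2.81, power 78%.

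**Range over ρ** (simulation, 40,000 trials per value, in line with the formulas):

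| ρ | ANCOVA, 3 arms | t-test, change | t-test, Week 12 score |
|---|---|---|---|
| 0.1 | 67% | 43% | 66% |
| 0.3 | 70% | 52% | 66% |
| 0.5 | 78% | 66% | 66% |
| 0.7 | 91% | 87% | 66% |
| 0.9 | 100% | 100% | 66% |

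With no treatment effect, every method rejected in 4.8% to 5.2% of trials.

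**Smaller effect.** At 0.8 SD and ρ = 0.3 / 0.5 / 0.7, ANCOVA gives 60.1 / 68.4 / 84.1%, change 43.2 / 56.2 / 77.9%, and the Week 12 score 56.2% throughout. At ρ = 0 the three-arm ANCOVA loses about 0.1 point to the Week 12 score (56.1% v 56.2%). A two-arm ANCOVA loses about 1.7 (54.5%).

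**Coarse scoring.** FASI is built from a few integer grades. Assume a simple sum of erythema 0–4, size 0–4 and extension 0/2/3, a baseline total of 7 to 11, and a 0.9 SD effect on the Week 12 score:

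| Observed correlation | ANCOVA | Percent change | Change | Week 12 score |
|---|---|---|---|---|
| 0.28 | 69.5% | 64.1% | 60.9% | 65.7% |
| 0.45 | 75.0% | 72.7% | 70.2% | 66.1% |
| 0.59 | 82.8% | 82.0% | 80.4% | 66.2% |
| 0.69 | 90.0% | 90.1% | 89.3% | 66.0% |

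By subtraction, ANCOVA gains about 4 to 24 points over the Week 12 score, 1 to 9 over change and 0 to 5 over percent change.

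**Unequal spread.** If response varies between subjects so that the active-arm SD is about 1.35 times placebo, then at correlations of 0.29 / 0.45 / 0.69 the three-arm ANCOVA gives 66 / 70 / 80%. The best t-test gives 66 / 71 / 84%, a loss of 0 to 4 points. ANCOVA on only the two arms compared gives 68 / 72 / 83%.

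**The case against.** The strongest reply is that nothing here is an error. An unadjusted t-test in a randomised trial is valid, the trial is declared exploratory, and no listed endpoint is a continuous FASI score. That stands, and it limits the point to an optional improvement.

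A second reply is that the benefit depends on the comparator. Both listed FASI endpoints are percent improvements, so percent change is a natural reading of what would be tested, and against it the modelled gain is only about 0 to 5 points. That also stands. The effect size, the correlations, the sum formula and the baseline floor are all assumed.

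A third reply is that removing the t-test sentence would leave other continuous variables without a stated test, such as the target-lesion volume and colour changes in Section 7.3.6.1. That is correct, so the fix adds a sentence and removes nothing.

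Two stronger readings are tempting and not supported:
- A reader might infer that the t-test inflates false positives because small arms can start unequal. Averaged over randomisation, its error is 5%, the same as for ANCOVA.
- A reader might infer that the tested quantity can be chosen after seeing the data, since "No adjustments for multiplicity are planned" and, at Week 12, "The database will be locked and unblinded to assess for efficacy and safety". Section 8.1 commits to a final SAP before that lock, so the documents do not show a choice left open at unblinding.

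**Conclusion.** The point holds as a suggestion to consider. The plan uses an unadjusted t-test where a baseline-adjusted model could use a value already collected, and it does not name the FASI quantity tested. Under equal spread and normal data, three-arm ANCOVA is about as good as or better than either t-test whatever the correlation. With 15 per arm and a 0.9 SD effect, the gain over the better of the two t-tests is 70 − 66 = 4 points at ρ = 0.3, 78 − 66 = 12 at 0.5 and about 91 − 87 = 4 at 0.7. On coarse scoring the gain over percent change is about 0 to 5 points, and under markedly uneven response up to about 4 points may be lost. It would be wrong to read this as a validity problem or as affecting the primary endpoint. If the SAP already names the quantity and a baseline covariate, the point is closed.

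**What to change.** In Section 8.5.2, the synopsis and the SAP, before the Week 12 lock:
- Keep the t-test sentence for other continuous variables.
- Add that FASI at Week 12, and at Week 4, is compared by ANCOVA on the observed score at that visit, with treatment (three arms) and Visit 2 FASI as covariate, reporting pairwise differences with 95% confidence intervals. Naming Visit 2 matters because FASI is also scored at Screening.
- Keep change and percent change as descriptive summaries.
- Prespecify the same model on only the two arms compared as the sensitivity analysis for unequal spread.

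The SAP should also say whether site, the stratification factor, enters the model; the figures here are without it.

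The cost is wording. No new data, visits or subjects are needed, and the model is standard in the planned software. The statistical price is the assumption of a common linear slope, a gain near zero over the Week 12 score at very low correlation and over change at very high correlation, and the possible loss under unequal spread.

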8.6 Analysis of Safety

The assessment of safety will be based mainly on the frequency of AEs and on the number of laboratory values that fall outside of predetermined ranges. Adverse events will be presented in data listings and summarized by frequency and severity for each treatment group. Laboratory and vital sign data will be presented in data listings. Abnormal laboratory findings will be presented. The analysis of safety will be described in the SAP.

8.6.1 Adverse Events

Adverse events will be summarized by presenting, for each treatment group, the number and percentage of subjects having any AE, having an AE in an individual body system, and having each individual AE. Any other information collected (e.g., severity or relatedness to study medication) will be listed as appropriate.

Adverse events will be summarized by the Medical Dictionary for Regulatory Activities (MedDRA) system organ class and preferred term. The incidence of AEs (percent of subjects reporting the AE at least once) will be tabulated separately for each treatment group by severity and relationship to drug.

8.6.2 Other Safety Variables

Clinical laboratory values will be reported as complete listings of individual subject data. Clinical laboratory data will be summarized by presenting shift tables using extended normal ranges (baseline to most extreme post-baseline value), by presenting summary statistics of raw data and change from baseline values (means, medians, standard deviations, ranges), and by the flagging of notable values in data listings.

Data from other tests (e.g., vital signs, special tests) will be considered as appropriate and listed. Notable values will be flagged, and any other information collected will be listed as appropriate. Any statistical tests performed to explore the data will be used only to highlight any interesting comparisons that may warrant further consideration.

8.7 Quality of Life Analysis

Not applicable.

9.0 CHANGES IN THE PLANNED STUDY

9.1 Protocol Amendments

With the exception of administrative changes, any changes or additions to this clinical study protocol require a written protocol amendment that must be approved by the sponsor, the Contract Research Organization (CRO), and the investigator(s) before implementation. Amendments significantly affecting the safety of subjects, the scope of the investigation, or the scientific quality of the study, require additional approval by the IRB for each study center.

These requirements for approval should in no way prevent any immediate action from being taken by the investigator or the sponsor in the interests of preserving the safety of all subjects included in the trial. If an immediate change to the protocol is felt to be necessary by the investigator and is implemented for safety reasons, the sponsor should be notified and the IRB should be informed according to their reporting requirements.

9.2 Termination or Suspension of the Study

The sponsor reserves the right to terminate or suspend the study at any time or a subject's participation due to a protocol amendment. In case of premature termination or suspension of the study, the CRO project manager will promptly inform the investigators, regulatory authorities, and IRBs about the premature termination or suspension, including the reason for it. In terminating the study, the sponsor and the investigator will ensure that adequate consideration is given to the protection of the subjects' interests.

10.0 DATA HANDLING AND RECORD KEEPING

10.1 Recording of Data

10.1.1 Source Documents

Source data are all the information in original records and copies of original records of clinical findings, observations, or other activities in the study, which are necessary for the reconstruction and evaluation of the study. The identification of any data to be recorded directly on the CRFs is to be considered source data.

Study data collection procedures must ensure that each data element can be traced with a high level of confidence from its originator or recorder to its representation in the study database and then to its place in the analysis and report of study results. Once recorded, the study data must be protected from unauthorized modification or deletion, and all authorized modifications and deletions must be securely linked in the permanent record with their author, time of change, and reason for change (i.e., the audit trail must be maintained).

The investigator will permit study-related monitoring, audit(s), IRB/IEC review(s) and regulatory inspection(s), with direct access to all the required source records.

The principal investigator will certify the data to be accurate and complete and will release the data for transmittal to the sponsor or CRO.

Source records need to be preserved for the maximum period of time permitted by local requirements (see [Section 10.2](#)). For each subject enrolled, the investigator will indicate in the source record(s) that the subject participated in the study.

10.1.2 Case Report Forms

The primary data collection tool for the study is an electronic case report form (eCRF) designed specifically for the study. For each subject enrolled in the study, an eCRF will be completed by the study coordinator and signed by the investigator or his/her designate.

The investigator will be responsible for ensuring the accuracy of all data entered in the eCRFs. All eCRFs are to be completed in a timely manner.

Errors occurring in the eCRFs will be queried. Queries raised by data reviewers must be addressed by site personnel.

On request, the investigator will provide the sponsor with additional data relating to the study, or copies of relevant source records, duly anonymized (i.e., subject's name is redacted).

10.2 Retention of Documents

The United States Food and Drug Administration (FDA)/ ICH regulations require all investigators participating in clinical drug trials to maintain detailed clinical data for one of the following periods:

- at least two years following the date on which a Marketing Application is approved by the FDA/applicable regulatory or health authority, or
- two years after the sponsor notifies the investigator that no further application is to be filed with the health authorities

Similarly, ICH guidelines require that essential documents be retained until at least two years after the last approval of a marketing application in an ICH region and until there are no pending or contemplated marketing applications in an ICH region, or at least 2 years have elapsed since the formal discontinuation of clinical development of the investigational product. European Union (EU) Directive 2001/63/EC requires that essential documents be retained for at least 15 years after completion or discontinuation of the trial.

To comply with these requirements, the investigator will not dispose of any records relevant to this study without either (1) written permission from the sponsor, or (2) providing an opportunity for the sponsor to collect such records. The investigator shall take responsibility for maintaining adequate and accurate hard copy source documents of all observations and data generated during this study, including any data clarification forms received from the sponsor. Such documentation is subject to inspection by the sponsor or its agents, the FDA and/or other regulatory agencies.

